# 6.3 Duration of Therapy

In the absence of treatment delays due to adverse events, treatment may continue indefinitely until one of the following criteria applies:

- Disease progression per RECIST version 1.
- The investigator considers it, for safety reasons, to be in the best interest of the patient.
- Unacceptable adverse event(s) related to treatment, defined as a grade 3 or 4 toxicity (per CTCAE v 4.03) that fails to recover to < Grade 2 in the absence of treatment within 4 weeks
- General or specific changes in the patient's condition render the patient unacceptable for further treatment in the judgment of the investigator
- Patient decision to withdraw from treatment (partial consent) or from the study (full consent)
- Pregnancy during the course of the study for a child-bearing participant

The date and reason for discontinuation must be documented. Every effort should be made to complete the appropriate assessments.

If in the opinion of the investigator, the patient demonstrates disease progression by RECIST, but the patient is demonstrating obvious clinical benefit to sunitinib therapy, the investigator may choose to continue patient on study. At the time that clinical benefit from study drug is no longer apparent, investigator will take patient off study and off study drug.

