#### 7.0 DOSING DELAYS / DOSE MODIFICATIONS

#### **Table 3: Dose/Schedule Levels**

Table 3a defines treatment levels of sunitinib with dose and schedule specifications. The starting dose for all patients will be 50 mg on a 2/1 schedule. Dosing schedule may be changed to 50 mg 1 week on followed by 3 days off alternating with 1 week on and 4 days off and repeated for a 6-week cycle at outlined in table 3a for toxicities described in table 3b. Patient requiring further reduction in treatment level will be dose reduced to 37.5 mg on a 2/1 schedule, and so on per table 3a. Intra-patient re-escalation back to the previous treatment level is permitted in the absence of grade  $\geq 3$  hematologic or grade  $\geq 2$  non-hematologic treatment-related toxicity in the previous cycle. Table 3b outlines indications for withholding treatment and for reductions in treatment levels.

Treatment Level	Sunitinib dose	Schedule
Level 0 (starting dose)	50 mg	2 weeks on/ 1 week off
Level -1	50 mg	1 week on/ 3 days off alternating with 1 week on/4 days off
Level -2	37.5 mg	2 weeks on/ 1 week off
Level -3	37.5 mg	1 week on/3 days off alternating with 1 week on/4 days off
Level -4	25 mg	2 weeks on/ 1 week off
Level -5	25 mg	1 week on/3 days off alternating with 1 week on/4 days off

Table 3a: Treatment levels of sunitinib with dose and schedule specifications

Table 3b: Indications for withholding treatment and reductions in treatment levels

Grade	Туре	Management/Next Dose for Sunitinib
≤ Grade 1 +	Any except vascular +	No change in treatment level
	Hematologic	Continue at same treatment level
Grade 2	Cardiac	Continue at same treatment level except in the event of:  -Decrease of LVEF by an absolute value of 20% and to below the lower limit of normal -Non-urgent ventricular paroxysmal dysrhythmia requiring intervention.  In these cases: withhold dose until toxicity is grade ≤1, then reduce the treatment by 1 level and resume treatment. If the patient was on level 0, then need to
-	N. 1' 1	resume at level -2
	Non-cardiac and non- hematologic	Continue at same dose level
	Hematologic***	Withhold dose until ANC>1,000 and Platelets > 50,000, then resume treatment at the same level or reduce by 1 level at the discretion of the investigator.
Grade 3	Cardiac	Withhold dose until toxicity is grade ≤1 or has returned to baseline, then resume treatment at the same level or reduce the dose by 1 level at the discretion of the investigator.**

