	Non-cardiac and non- hematologic*	Withhold dose until toxicity is grade $\leq 1$ or has returned to baseline, then resume treatment at the same level or reduce by 1 level at the discretion of the investigator.
	Hematologic***	Withhold dose until toxicity is grade ≤1 or has returned to baseline, then reduce by 1 level and resume treatment**.
Grade	Cardiac	Remove from protocol.
4	Non-cardiac and non- hematologic	Withhold dose until toxicity is grade ≤1 or has returned to baseline, then reduce by 1 level and resume treatment, or discontinue at the discretion of the investigator.

<sup>+Except vascular- for all vascular toxicities, including grade 1, drug must be held and appropriate treatment initiated. Sunitinib may be restarted at the discretion of the treating MD.

All intra-patient dose reductions are relative to the lowest dose level of the current cycle. If the current treatment level is -5 and the toxicity guidelines above indicate a further treatment/dose reduction is necessary, treatment should be discontinued. Patients are to be removed from study if toxicity does not resolve to grade 1 or less within

\* Patients with grade 3 asymptomatic biochemistry laboratory abnormalities may continue treatment at the same dose level without interruption at the discretion of the investigator.

\*\* Hypertension may be managed appropriately with anti-hypertensives, and the patient may continue sunitinib provided the blood pressure is controlled to < 160/90 mmHg within 4 weeks. Patients who are unable to have blood pressure controlled to < 160/90 mmHg within 4 weeks should be removed from the study. **Patients with congestive heart failure must be removed from study.** 

\*\*\*Patients who develop grade 3 or 4 lymphopenia may continue study treatment without interruption.

4 weeks off study drug.

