#### 16.5 Analytic plan for secondary objectives:

- PFS will be measured from the date of initiation of treatment to the first of documented progression or death; and will be estimated using the Kaplan-Meier method. PFS is expected to be comparable to that seen with 4/2 (11 month median); however if the upper bound of the interval is less than 8 months this will be taken as an indication that the efficacy of 2/1 is inferior to that of 4/2.
- Toxicities will be tabulated by type and grade, and the incidence of all  $\geq$  grade 3 toxicities will be calculated by CTCAE v 4.03 along with a 95% confidence interval
- The percentage of patients who underwent one or more dose reductions, dose interruptions and/or treatment delays will be estimated along with a 95% confidence interval. The number of patients who discontinue treatment due to unacceptable toxicities will be recorded, and reported as a percentage of the total number of enrolled patients along with 95% confidence interval.
- Health-related quality of life (HRQOL) will be assessed by FACT-G questionnaires as a secondary endpoint. Questionnaires will be administered at baseline, week 12, week 24 and week 36. Descriptive summary statistics will be calculated for all continuous variables (means, standard deviations, medians, ranges, percentage of patients scoring in the highest category for each item) for the items in the subscales each time point. The mean trajectories of each group over time will be plotted for the total scores, along with scores for physical well-being, emotional well-being, functional well-being, and renal-specific scales for FACT-G.

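### Table 3b's restart criteria do not match the stop rules in Sections 6.3 and 7, so a patient still off drug at about week 4 can be told both to resume and to stop

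*Combined protocol and SAP*

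**What the plan says.** Restart rules, protocol Section 7.0, Table 3b:

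- Grade 3 hematologic: "Withhold dose until ANC>1,000 and Platelets > 50,000, then resume treatment at the same level or reduce by 1 level", at the investigator's discretion.
- Grade 3 cardiac, and in substance grade 3 non-cardiac and non-hematologic: "Withhold dose until toxicity is grade ≤1 or has returned to baseline, then resume treatment at the same level", or one level lower.
- Grade 4 hematologic, and grade 4 non-cardiac and non-hematologic: "Withhold dose until toxicity is grade ≤1 or has returned to baseline, then reduce by 1 level and resume treatment". The second of these rows also allows discontinuation.
- Grade 4 cardiac: removal, so no restart question arises.
- A footnote to the hematologic rows adds: "Patients who develop grade 3 or 4 lymphopenia may continue study treatment without interruption". Another lets asymptomatic grade 3 biochemistry abnormalities continue without a hold.

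Stop rules:

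- Section 6.3 ends treatment for an unacceptable treatment-related event, defined as a grade 3 or 4 toxicity "that fails to recover to < Grade 2 in the absence of treatment within 4 weeks".
- The closing paragraph of Section 7 reads "Patients are to be removed from study if toxicity does not resolve to grade 1 or less within" "4 weeks off study drug".

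Endpoint, Sections 16.2 and 16.5: "The number of patients who discontinue treatment due to unacceptable toxicities will be recorded". It is reported as a percentage of all enrolled patients; Section 16.3 plans 60.

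**The concern.** Restart and removal should turn on the same recovery standard. Here Table 3b accepts two outcomes that the stop rules do not recognise: counts above fixed ANC and platelet values, and return to a baseline that may itself be above grade 1. Nothing says which passage governs when they disagree.

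What is at stake is mainly an endpoint definition. Section 6.3 contains the protocol's only definition of an unacceptable adverse event, and discontinuation for unacceptable toxicity is a secondary endpoint. If sites in this multicenter trial follow different passages for the same clinical picture, the reported rate partly reflects how the text was read. Section 7 also takes the patient off study and not only off drug. Section 6.4 provides 30 days of toxicity follow-up and Section 16.5 gives no censoring rule for PFS, so observation of progression could be shortened as well.

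**Working it through.** The plan states no figure on this point, so there is none to reproduce. The check sets the rules side by side and asks, case by case, whether they give different instructions.

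**Recovery standard in each place**

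- Table 3b, grade 3 hematologic: ANC >1,000 and platelets >50,000. The row gives no grade and no time limit.
- Table 3b, grade 3 cardiac, grade 3 other, grade 4 hematologic, grade 4 other: grade ≤1 or return to baseline. The rows give no time limit.
- Section 6.3: below grade 2, that is grade ≤1, within 4 weeks without treatment. It covers treatment-related grade 3 or 4 events and ends treatment.
- Section 7, closing paragraph: grade ≤1 within 4 weeks off drug. It covers toxicity with no grade named and removes the patient from study.

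The two stop rules agree on the grade. They differ from each other in scope and consequence, and both differ from Table 3b on the standard.

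**Do the looser criteria really reach beyond grade 1?**

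- Return to baseline adds something to grade ≤1 only if the baseline was above grade 1. No CTCAE table is needed to see that. The stop rules give no effect to the alternative in exactly those patients.
- The documents print no CTCAE cut-points. That counts just above 1,000 and 50,000 are still above grade 1 is inferred from Table 3b, which uses these values as the exit from grade 3 and gives grade 4 events a separate grade ≤1 criterion.

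**Cases**

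1. The Table 3b criterion is met before week 4, with toxicity still above grade 1. Table 3b allows restart. The patient is then no longer off drug, so on a literal reading neither stop rule is reached. There is no contradiction unless the clock is held to run on after restart, and the text does not settle that.
2. The Table 3b criterion is not met by week 4. Table 3b does not call for restart and the stop rules apply. There is no contradiction.
3. The patient is still off drug at about week 4, meets the ANC and platelet values or is back at baseline, and is not at grade ≤1. Table 3b says resume; Sections 6.3 and 7 say stop. The contradiction is direct.
4. A footnote allows treatment to continue (lymphopenia, asymptomatic grade 3 biochemistry) and this is used. No hold starts and there is no contradiction.

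Case 3 is plausible. After Cycle 1 Day 1, the study calendar and Section 12.2 schedule visits and laboratory tests at Day 42 of each cycle, and they may be every 12 weeks after cycle 12. No laboratory schedule during a hold is given, so recovery may first be documented near or after week 4. The text is also silent on whether planned off-drug weeks count toward the four.

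**Anemia.** The grade 3 hematologic row releases the hold on ANC and platelets only. For grade 3 anemia those values say nothing about recovery.

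**Size.** With 60 patients as denominator, one patient classified differently moves the discontinuation rate by 1/60 = 0.0167, or 1.7 percentage points.

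**The case against.** The strongest reply is that both stop rules need four weeks without drug. Anyone who meets the looser criterion sooner restarts and never reaches them; anyone who never meets it stops under every passage. A reader might infer that every patient restarted on the looser criterion must also be removed. The documents do not support that: the off-drug condition confines the conflict to case 3, or to an unstated reading in which the clock continues after restart.

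Three further replies carry weight.

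- Holding drug until counts recover implies that counts are repeated during the hold, so late documentation may be uncommon. That is fair, but no recheck schedule is written.
- Section 6.3 is limited to treatment-related events, so a return to a pre-existing abnormality could be read as resolved toxicity. That is a sensible reading of 6.3, but it is not stated, and the closing sentence of Section 7 has no such limit.
- Different restart thresholds for grade 3 and grade 4 hematologic events are not in themselves an inconsistency. That is accepted; the point concerns restart against removal.

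A reader might also infer that a patient with grade 3 anemia is released at once and still removed under Section 7. That does not follow: if the hold ends at once, four weeks off drug never accrue. What remains is that the row lacks a criterion fitting anemia.

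**Conclusion.** The point stands in a limited form. Table 3b and the two stop rules use different recovery standards, and a patient still off drug at about week 4 who meets the first but not the second receives opposite instructions. The status of the clock after an earlier restart is undefined.

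The number of such patients cannot be derived from the documents and is probably small. A reader might take Table 1's grade 3+ low-platelet rates, 9% to 16% on sunitinib in the three larger trials, and infer up to 16% x 60 = 9.6 patients in conflict. That is not supported. Those figures count everyone with the event, may include grade 4 events that follow a different row, and say nothing about who is still off drug at week 4; the 30-patient 2/1 series shows 0%. Only the per-patient effect of 1.7 points can be stated.

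Nor does the mismatch change whether a primary-endpoint event that has already occurred is counted. Section 16.1 counts a patient once a related grade ≥3 fatigue, hand-foot syndrome or diarrhea event occurs; at most, later exposure changes.

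The conclusion rests on two assumptions: that counts just above the restart values are above grade 1, as Table 3b implies, and, for the baseline route, that some patients enter with a value above grade 1. The documents give no frequency for the latter.

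**What to change.** Reconcile Section 6.3, Table 3b and the closing paragraph of Section 7 so that restart and removal use one recovery criterion in each row. The amended text should state:

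- whether return to baseline counts as recovery for the removal rules;
- which recovery criterion applies to grade 3 hematologic events, including one that fits anemia;
- when the four-week clock starts and stops, including whether a restart ends it;
- whether the rule ends treatment or removes the patient from study, and for which events.

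The same definition should then be used for discontinuation due to unacceptable toxicity in Sections 16.2 and 16.5. The choice of criterion belongs to the sponsor's clinicians. The cost is a wording amendment, with no added visits, data or patients.

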# 8.0 ADVERSE EVENTS: LIST AND REPORTING REQUIREMENTS

The following is a list of AEs (Section 8.1) and the reporting requirements associated with observed AEs (Sections 8.3 and 8.4).

The clinical course of each event will be followed until resolution, stabilization, or until it has been determined that the study treatment or participation is not the cause.

Serious adverse events that are still ongoing at the end of the study period will necessitate follow-up to determine the final outcome. Any serious adverse event that occurs after the study period and is considered to be possibly related to the study treatment or study participation will be recorded and reported immediately.

- 8.1 Adverse Events and Potential Risks
- 8.1.1 Adverse events and potential risks list

Adverse events will be assessed and will be graded according to the NCI CTCAE v4.03. CTCAE v4.3 can be accessed on the internet at: http://evs.nci.nih.gov/ftp1/CTCAE/CTCAE 4.03 2010-06-14 QuickReference 8.5x11.pdf. All toxicities \geq Grade 4, unexpected AND drug related should be reported (using a MedWatch form) to the Principal Investigator, the Data Safety and Toxicity Committee and the IRB.

To date, over 1500 subjects with advanced malignancies have been treated with sunitinib malate. Multiple phase 1, 2 and 3 studies have been conducted or are underway. Study subjects enrolled on the initial clinical studies received sunitinib malate in a free-base formulation, but study subjects enrolled on protocols activated after February 2002 were treated with the sunitinib malate salt formulation. A prior study demonstrated the bioequivalence of these 2 formulations.

The primary DLT in the phase 1 studies appeared to be fatigue/asthenia, which generally occurred 10 to 15 days after start of therapy, and was readily reversible upon discontinuation of sunitinib malate treatment. Fatigue appeared to increase in frequency with an increase in drug exposure. DLT experienced during the first cycle of therapy was observed more frequently in subjects on Schedule 4/2 than in subjects on Schedule 2/2. Overall, the most frequent adverse events associated with sunitinib malate treatment of greatest severity have been constitutional (fatigue/asthenia), gastrointestinal (nausea, vomiting, diarrhea), and hematologic (neutropenia, thrombocytopenia). The degree of adverse event severity appears to correlate with higher drug exposure and/or lower subject performance status. A similar pattern was observed for subjects with previous chemotherapy in comparison to chemotherapy-naïve subjects.

In studies evaluating starting doses that ranged from 75 to 100 mg daily, cardiac hypokinesis and clinical signs of congestive heart failure were reported in 4 of 62 advanced acute myeloid leukemia subjects; however, the causal relationship to sunitinib malate was confounded by disease morbidities and prior anthracycline exposure. At the 50-mg dose level, asymptomatic

decreases in cardiac ejection fraction were observed in <5% of solid tumor subjects, either with or without a prior history of cardiovascular disease or anthracycline exposure. Decrease in LVEF by MUGA is reversible and does not appear to have cumulative effect with repeat drug exposure. A review of cardiac and other safety data from clinical and preclinical studies is provided in the Investigator Brochure.

The maximum tolerated dose has been defined as 50 mg in phase 1 clinical studies in subjects with advanced solid tumors, subjects with AML, and subjects with imatinib mesylate-resistant GIST. Subjects receiving this dose of sunitinib malate achieved target plasma concentrations of sunitinib malate plus SU012662 in the range of 50 to 100 ng/mL.

#### 8.2 Definitions

#### 8.2.1 Adverse Events

An **adverse event** (AE) is any unfavorable or unintended event, physical or psychological, associated with a research study, which causes harm or injury to a research participant as a result of the participant's involvement in a research study. The event can include abnormal laboratory findings, symptoms, or disease associated with the research study. The event does not necessarily have to have a causal relationship with the research, any risk associated with the research, the research intervention, or the research assessments.

Adverse events may be the result of the interventions and interactions used in the research; the collection of identifiable private information in the research; an underlying disease, disorder, or condition of the subject; and/or other circumstances unrelated to the research or any underlying disease, disorder, or condition of the subject. In general, adverse events that are at least partially the result of (a) or (b) would be considered related to the research, whereas adverse events solely related to (c) or (d) would be considered unrelated to the research.

**External adverse events** are adverse events experienced by subjects enrolled in multicenter clinical trials at sites other than the site(s) over which the Institutional Review Board has jurisdiction.

**Internal adverse events** are adverse events experienced by subjects enrolled at the site(s) under the IRB's jurisdiction for either multicenter or single-center research projects.

The significance of an adverse event is used to describe the patient/event outcome or action criteria associated with events that pose a threat to a patient's life or functioning (i.e., moderate, severe or life threatening). Based on the National Cancer Institute Guidelines for the Cancer Therapy Evaluation Program, severity can be defined by the following grades of events:

**Grades 1** are mild adverse events. (e.g., minor event requiring no specific medical intervention; asymptomatic laboratory findings only; marginal clinical relevance)

**Grades 2** are moderate adverse events (e.g., minimal intervention; local intervention; non-invasive intervention; transfusion; elective interventional radiological procedure; therapeutic endoscopy or operation).

**Grades 3** are severe and undesirable adverse events (e.g., significant symptoms requiring hospitalization or invasive intervention; transfusion; elective interventional radiological procedure; therapeutic endoscopy or operation).

**Grades 4** are life threatening or disabling adverse events (e.g., complicated by acute, life-threatening metabolic or cardiovascular complications such as circulatory failure, hemorrhage, sepsis; life-threatening physiologic consequences; need for intensive care or emergent invasive procedure; emergent interventional radiological procedure, therapeutic endoscopy or operation).

**Grades 5** are fatal adverse event resulting in death.

#### 8.2.2 Serious Adverse Events

An adverse event or suspected adverse reaction is considered "serious" if, in the view of either the investigator or the sponsor, it results in any of the following outcomes:

- Death
- A life-threatening adverse drug experience any adverse experience that places the patient, in the view of the initial reporter, at immediate risk of death from the adverse experience as it occurred. It does not include an adverse experience that, had it occurred in a more severe form, might have caused death.
- Inpatient hospitalization or prolongation of existing hospitalization
- A persistent or significant incapacity or substantial disruption of the ability to conduct normal life functions.
- A congenital anomaly/birth defect.

